12.0 DATA REPORTING / REGULATORY REQUIREMENTS

All IRB and FDA reporting requirements will be followed per applicable FDA regulations.

Adverse events will be reported by the treating physician or other research team members to the principal investigator. The sponsor/principal investigator is responsible for filing reports to the FDA and IRB as required.

All adverse events will be reviewed by the medical monitor at Norton Healthcare.

This study will be registered on clinicaltrials.gov.

Study endpoints (e.g., mortality or major morbidity) must be reported to FDA by the sponsor investigator as described in the protocol and ordinarily would not be reported under paragraph 21 CFR 312.32(c).

13.0 ADVERSE EVENTS AND REPORTING REQUIREMENTS

Serious Adverse Events and Transfusion Reactions will be collected from the time of informed consent until the subject is discharged or dies.

The following information about the event will be documented: event, start and resolution date (and time if known), treatments received, and outcome.

The event will be reviewed by the Sponsor/Principal Investigator to determine severity and causality to the convalescent plasma infusion.

SAEs will be reported to the FDA and IRB as required. SAEs include those events that result in death, life-threatening adverse event, inpatient hospitalization or prolongation of existing hospitalization, persistent or significant incapacity or substantial disruption of the ability to conduct normal life functions, or a congenital anomaly/birth defect, or other important medical event that may jeopardize the subject or may require intervention to prevent one of the outcomes included in this definition.

ADVERSE EVENT DEFINITIONS

The following definitions regarding adverse events, as defined by 21 CFR 312.32(a), will be used for this protocol.

Adverse event - Any untoward medical occurrence associated with the use of a drug in humans, whether or not considered drug related.

Life-threatening adverse event or life-threatening suspected adverse reaction - An adverse event or suspected adverse reaction is considered "life-threatening" if, in the view of either the investigator or sponsor, its occurrence places the patient or subject at immediate risk of death. It does not include an adverse event or suspected adverse reaction that, had it occurred in a more severe form, might have caused death.

Serious adverse event or serious suspected adverse reaction - An adverse event or suspected adverse reaction is considered "serious" if, in the view of either the investigator or sponsor, it results in any of the following outcomes: Death, a life-threatening adverse event, inpatient hospitalization or prolongation of existing hospitalization, a persistent or significant incapacity or substantial disruption of the ability to conduct normal life functions, or a congenital anomaly/birth defect. Important medical events that may not result in death, be life-threatening, or require hospitalization may be considered serious when, based upon appropriate medical judgment, they may jeopardize the patient or subject and may require medical or surgical intervention to prevent one of the outcomes listed in this definition. Examples of such medical events include allergic bronchospasm requiring intensive treatment in an emergency room or at home, blood dyscrasias or convulsions that do not result in inpatient hospitalization, or the development of drug dependency or drug abuse.

Suspected adverse reaction - Any adverse event for which there is a reasonable possibility that the drug caused the adverse event. For the purposes of IND safety reporting, "reasonable possibility" means there is evidence to suggest a causal relationship between the drug and the adverse event. Suspected adverse reaction implies a lesser degree of certainty about causality than adverse reaction, which means any adverse event caused by a drug.

Unexpected adverse event or unexpected suspected adverse reaction - An adverse event or suspected adverse reaction is considered "unexpected" if it is not listed in the investigator brochure or is not listed at the specificity or severity that has been observed; or, if an investigator brochure is not required or available, is not consistent with the risk information described in the general investigational plan or elsewhere in the current application, as amended. For example, under this definition, hepatic necrosis would be unexpected (by virtue of greater severity) if the investigator brochure referred only to elevated hepatic enzymes or hepatitis. Similarly, cerebral thromboembolism and cerebral vasculitis would be unexpected (by virtue of greater specificity) if the investigator brochure listed only cerebral vascular accidents. "Unexpected," as used in this definition, also refers to adverse events or suspected adverse reactions that are mentioned in the investigator brochure as occurring with a class of drugs or as anticipated from the pharmacological properties of the drug, but are not specifically mentioned as occurring with the particular drug under investigation.

Unexpected fatal or life-threatening suspected adverse reaction reports - The sponsor must also notify FDA of any unexpected fatal or life-threatening suspected adverse reaction as soon as possible but in no case later than 7 calendar days after the sponsor's initial receipt of the information.

REVIEW OF SAFETY INFORMATION

The sponsor investigator must promptly review all information relevant to the safety of the drug obtained or otherwise received by the sponsor investigator from foreign or domestic sources, including information derived from any clinical or epidemiological investigations, animal or in vitro studies, reports in the scientific literature, and unpublished scientific papers, as well as reports from foreign regulatory authorities and reports of foreign commercial marketing experience for drugs that are not marketed in the United States.

IND SAFETY REPORTS

The sponsor investigator must notify FDA and all participating investigators (i.e., all investigators to whom the sponsor investigator is providing drug under in an IND safety report of potential serious risks, from clinical trials or any other source, as soon as possible, but in no case later than 15 calendar days after the sponsor investigator determines that the information qualifies for reporting under paragraph 21 CFR 312.32 (c)(1)(i), (c)(1)(ii), (c)(1)(iii), or (c)(1)(iv) of this section. In each IND safety report, the sponsor investigator must identify all IND safety reports previously submitted to FDA concerning a similar suspected adverse reaction, and must analyze the significance of the suspected adverse reaction in light of previous, similar reports or any other relevant information.

REPORTING REQUIREMENTS

Serious and unexpected suspected adverse reaction - The sponsor investigator must report any suspected adverse reaction that is both serious and unexpected. The sponsor investigator must report an adverse event as a suspected adverse reaction only if there is evidence to suggest a causal relationship between the drug and the adverse event, such as:

- A single occurrence of an event that is uncommon and known to be strongly associated with drug exposure (e.g., angioedema, hepatic injury, Stevens-Johnson Syndrome);
- One or more occurrences of an event that is not commonly associated with drug exposure, but is otherwise uncommon in the population exposed to the drug (e.g., tendon rupture);
- An aggregate analysis of specific events observed in a clinical trial (such as known consequences of the underlying disease or condition under investigation or other events that commonly occur in the study population independent of drug therapy) that indicates those events occur more frequently in the drug treatment group than in a concurrent or historical control group.

If a serious and unexpected adverse event occurs for which there is evidence suggesting a causal relationship between the drug and the event (e.g., death from anaphylaxis), the event must be reported under 312.32(c)(1)(i) as a serious and unexpected suspected adverse reaction even if it is a component of the study endpoint (e.g., all-cause mortality).

Findings from other studies - The sponsor investigator must report any findings from epidemiological studies, pooled analysis of multiple studies, or clinical studies (other than those reported under paragraph 21 CFR 312.32(c)(1)(i) of this section), whether or not conducted

under an IND, and whether or not conducted by the sponsor investigator, that suggest a significant risk in humans exposed to the drug. Ordinarily, such a finding would result in a safety-related change in the protocol, informed consent, investigator brochure (excluding routine updates of these documents), or other aspects of the overall conduct of the clinical investigation.

Findings from animal or in vitro testing - The sponsor investigator must report any findings from animal or in vitro testing, whether or not conducted by the sponsor investigator, that suggest a significant risk in humans exposed to the drug, such as reports of mutagenicity, teratogenicity, or carcinogenicity, or reports of significant organ toxicity at or near the expected human exposure. Ordinarily, any such findings would result in a safety-related change in the protocol, informed consent, investigator brochure (excluding routine updates of these documents), or other aspects of the overall conduct of the clinical investigation.

Increased rate of occurrence of serious suspected adverse reactions - The sponsor investigator must report any clinically important increase in the rate of a serious suspected adverse reaction over that listed in the protocol or investigator brochure.

Submission of IND safety reports - The sponsor investigator must submit each IND safety report in a narrative format or on FDA Form 3500A or in an electronic format that FDA can process, review, and archive. Reports of overall findings or pooled analyses from published and unpublished in vitro, animal, epidemiological, or clinical studies must be submitted in a narrative format. Each notification to FDA must bear prominent identification of its contents, i.e., "IND Safety Report," and must be transmitted to the review division in the Center for Drug Evaluation and Research or in the Center for Biologics Evaluation and Research that has responsibility for review of the IND. Upon request from FDA, the sponsor investigator must submit to FDA any additional data or information that the agency deems necessary, as soon as possible, but in no case later than 15 calendar days after receiving the request.

FOLLOW-UP

- The sponsor investigator must promptly investigate all safety information it receives.
- Relevant follow up information to an IND safety report must be submitted as soon as the information is available and must be identified as such, i.e., "Followup IND Safety Report."
- If the results of a sponsor investigator's investigation show that an adverse event not initially determined to be reportable under paragraph (c) of this section is so reportable, the sponsor investigator must report such suspected adverse reaction in an IND safety report as soon as possible, but in no case later than 15 calendar days after the determination is made.

15.0 TABLE 1: DEFINING CHARACTERISTICS OF SEVERE COVID-19 DISEASE

Respiratory Frequency >30/min

Blood Oxygen Saturation < 93%

Partial Pressure of Arterial Oxygen to Fraction of Inspired Oxygen Ratio <300

Respiratory Failure

Septic Shock

Multiple Organ Dysfunction /Failure

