1.0 OBJECTIVES

1.1 Primary Objectives:

To determine the therapeutic efficacy (response rate) of convalescent plasma infusion in patients at high risk for mortality when infected by SARS-CoV-2 (COVID-19). The primary endpoint will be determined as prevention of progression to severe or life threatening COVID-19 during the current hospitalization. The primary endpoint will be assessed at discharge and by evaluating if the patient experienced the following data elements: respiratory rate >30/min, Blood oxygen saturation <93%, partial pressure of arterial oxygen to fraction of inspired oxygen ration <300, or received a medical diagnosis of respiratory failure, septic shock or multiple organ dysfunction/failure. This will be captured from the daily physical exam/clinical assessment done as part of routine care. See table 1.

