2.0 BACKGROUND AND RATIONALE

The morbidity and mortality of the SARS-CoV-2 (COVID-19) pandemic has been well established. Approaches to COVID-19 has focused on preventing mass spread and treating those with critical disease, while providing supportive care to mild, moderate or severe disease. The FDA has provided guidelines for the treatment of patients with convalescent plasma and this has been restricted to patients with severe or critical disease. As our understanding of the epidemiology of this syndrome continues to expand, it has become clearer that given the extremely poor outcome for those requiring mechanical ventilation and those within a few discreet categories, a therapeutic approach focused around prevention of the transition to critical status is a key to ameliorate the poor outcomes experienced to date.

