2.1 SARS-CoV-2 Infection (COVID-19)

The impact of the severe acute respiratory syndrome coronavirus - 2 (SARS-CoV-2) pandemic and more specifically the associated syndrome [COVID-19], has been rapid and extreme. As of June 1, 2020 estimates for worldwide spread suggests almost 6.3 million confirmed cases, 375,000 deaths and 1.8 million confirmed cases in the United States (GISANDDATA.maps.arcgis.com). Data continues to suggest that those at greatest risk for poor outcome include the elderly and those with comorbid illness((1)(2)(3)). In fact, Zhou reports in a retrospective multivariate analysis the odds of dying in the hospital related to COVID-19 was highest with increased age, Sequential Organ Failure Assessment (SOFA) score and concomitant markers of inflammation.(4) A report of 72,314 patients in China reports

the case fatality rate (CFR) of those over 80 years of age is 14.8%, as compared to the overall CFR of 2.3%. (5) In fact, 61.5% of those with critical disease died. (6)

There is an increasing understanding of the temporal seroconversion rate in patients infected by SARS-CoV-2 virus. Zhao and colleagues reported that among 173 patients tested median seroconversion time for IgM and IgG occurred on day 12 and day 14 respectively.(7) The relationship of this conversion timeline and the best timing of plasma procurement is still to be determined. Though this data allows that between day 14 and 21 seem optimal for plasma procurement, much of the timeliness is sure to be clarified in large multicenter trials.

Most recently, the United States Food and Drug Administration has published guidelines on the emergent use of convalescent plasma in the treatment of the COVID-19 patient.(8) It was made clear that patients with severe disease as measured by a laboratory confirmed COVID-19 infection, severe or immediately life threatening COVID-19 clinical presentation, with severe being consistent with presence of dyspnea, tachypnea (respiratory frequency $\geq 30/\text{min}$), blood oxygen saturation $\leq 93\%$, partial pressure of arterial oxygen to fraction of inspired oxygen ratio < 300 , and/or lung infiltrates $> 50\%$ within 24 to 48 hours may be eligible to receive convalescent plasma through an emergent IND protocol. In this definition, life threatening disease is defined as the presence of respiratory failure, septic shock or multiple organ dysfunction.(8)

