4.2.4 Respiratory rate >30/min

4.2.5 Blood oxygen saturation <93%

4.2.6 Partial pressure of arterial oxygen to fraction of inspired oxygen ration <300

4.2.7 Diagnosis of respiratory failure, septic shock or multiple organ dysfunction/failure

4.3 Inclusion of Women and Minorities

Both men and women of all races and ethnic groups are eligible for this trial.

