6.2 Supportive Care for Clinical Deterioration While on This Study

Due to the possibility of clinical worsening in the interim after infusion, full supportive measures should be undertaken. This includes ventilator support, adequate volume expansion and pressure support. Antimicrobials are allowed in accordance with institution standard procedures.

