11.0 STATISTICAL CONSIDERATIONS

11.1 Study Design / Endpoints

This study uses a standard descriptive statistics for outcomes.

To determine the therapeutic efficacy (response rate) of convalescent plasma infusion in patients at high risk for mortality when infected by SARS-CoV-2 (COVID-19). The primary endpoint will be determined as prevention of progression to severe or life threatening COVID-19 during the current hospitalization. The primary endpoint will be assessed at discharge and by evaluating if the patient experienced the following data elements: respiratory rate $>30/\text{min}$, Blood oxygen saturation $<93\%$, partial pressure of arterial oxygen to fraction of inspired oxygen ration <300 , or received a medical diagnosis of respiratory failure, septic shock or multiple organ dysfunction/failure. This will be captured from the daily physical exam/clinical assessment done as part of routine care. See table 1.

The secondary objectives are to:

- Determine the immunologic effects of convalescent plasma infusion as measured by serial SARS-CoV-2 Ag levels through RT-PCR. This will be measured by CoV PCR collected at enrollment, day 7 and discharge.
- To measure normalization of laboratory parameters for risk as referenced in Appendix 2. Lab values outlined in appendix 2 will be documented every 3 days while the patient is hospitalized and we will evaluate labs from the time of convalescent plasma infusion to the time that lab value returns to within the institution's normal range.

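### The primary endpoint does not count escalation to high-flow oxygen or ventilation as progression, although Appendix 2 already records it; one prespecified sensitivity analysis would cover the gap

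*Combined protocol and SAP*

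**What the plan says.** Sections 1.1 and 11.1 define success as no progression to severe or life-threatening disease by discharge. Both list the same elements: "respiratory rate >30/min, Blood oxygen saturation <93" per cent, a P/F ratio below 300, or a medical diagnosis of respiratory failure, septic shock or multiple organ dysfunction/failure. Table 1 repeats them, with saturation as "Blood Oxygen Saturation < 93" per cent. The data come from routine daily assessment.

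Sections 4.2.4 to 4.2.7 exclude patients who meet any of these elements at entry. Section 4.2 does not exclude patients already on oxygen.

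Appendix 2 records the highest respiratory rate and lowest saturation in each 24 hours, and the P/F ratio if there is one. It also records oxygen route, amount, start and stop dates, and whether a ventilator was ever needed, with dates on and off. Dated fields are provided for the three diagnoses after plasma.

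Section 2.0 motivates the trial partly by "the extremely poor outcome for those requiring mechanical ventilation". Section 6.2 describes full supportive care if the patient worsens: "This includes ventilator support, adequate volume expansion and pressure support".

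Section 11.2 gives a maximum accrual of 100 and plans summary statistics with no hypothesis test.

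**The concern.** Oxygen saturation depends on how much oxygen is given. A worsening patient can be held at or above 93% by more support. The element that allows for support is P/F, but it exists only when a blood gas is drawn, and section 10.0 leaves the overall frequency of testing to the treating team. The endpoint also has no element for the support itself. Whether an escalated patient counts as a failure can therefore depend on whether a gas was taken or a diagnosis charted, and not only on the patient's course.

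The response rate is the primary efficacy result of a study with no comparator arm and no test, so it will be read as it stands. A gap of this kind can only leave the rate equal to or higher than it would be if escalation counted.

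**Working it through.** There is no stated figure to reproduce: the plan gives no target rate, power or precision. The check is a comparison of fields, followed by a scale for the effect.

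**Step 1. Follow one patient through the endpoint.** The patient starts high-flow oxygen after infusion.

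| Item | Recorded in Appendix 2 | Counts as progression? |
|---|---|---|
| Respiratory rate | Daily highest | Only if above 30/min |
| Saturation | Daily lowest, no link to support | Only if below 93% |
| P/F ratio | If available | Only if a value exists and is below 300 |
| Respiratory failure, septic shock, multiple organ dysfunction | Dated diagnosis fields | Only if diagnosed |
| Oxygen route, amount, dates | Yes | No |
| Ventilator use, dates | Yes | No |

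The patient is a success if saturation never falls below 93%, rate never exceeds 30/min, no P/F value exists, and none of the three diagnoses is charted. All four must hold together.

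**Step 2. Scale.** Let n be the number of patients, S the successes under the primary definition, and k the successes with a new start of high-flow oxygen, non-invasive or mechanical ventilation. S and k are assumptions; the documents give neither.

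- Sensitivity rate = (S − k)/n.
- Each reclassified patient costs 100/n points: 100/100 = 1, 100/50 = 2, 100/25 = 4.

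At n = 100:

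| Assumed S | k = 1 | k = 5 | k = 10 |
|---|---|---|---|
| 50 | 49% | 45% | 40% |
| 70 | 69% | 65% | 60% |
| 90 | 89% | 85% | 80% |

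For scale, the exact (Clopper-Pearson) 95% interval for 70/100 is 60.02% to 78.76%. This shows only how large the shifts are relative to the precision of the rate. Reclassifying the same patients is a change of definition, not sampling error.

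**Step 3. Can the analysis be done?** Yes. Infusion date, oxygen route with start and stop dates, and ventilator dates are all on the form. Two details need a rule. Oxygen and ventilator entries carry dates but no times, so an entry on the infusion day cannot be placed before or after the infusion. The ventilator question covers the whole hospitalization, so its date must be compared with the infusion date.

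**The case against.** The strongest case is that the existing elements close most of the gap. The form takes 24-hour extremes, so the desaturation that prompts escalation would often itself be a failure; as written, a single reading of 92% is enough. A ventilated patient will usually be given a diagnosis of respiratory failure, for which there is a dated field. Appendix 2 also has a free entry for blood gases. All of this stands, and it is why the point is minor. It does not remove the gap: the blood-gas entry helps only when a gas was drawn, and nothing in the protocol says that ventilation counts as progression. Section 7.1 even provides for consent on behalf of a patient on a ventilator, while 4.2.7 excludes respiratory failure. That may be template wording, but it means the two cannot simply be equated.

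It can also be said that the severity definition described in section 2.1 has no oxygen or ventilator element either. That is correct. The case here rests on the trial's stated purpose in 2.0 and 6.2, not on that definition.

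Finally, the study is descriptive and sets no target, so no formal decision turns on a few points. That also stands, though the rate remains the main result readers will see.

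A reader might go further and infer that the limits themselves are wrong, because section 2.1 reports a rate of 30/min or more and saturation of 93% or less. The documents do not support this. Section 2.1 reports, as background, who may receive plasma under emergency use. The trial's own limits are the same in 1.1, 11.1, Table 1 and the exclusions ("Respiratory rate >30/min" and "Blood oxygen saturation <93" per cent), so entry and outcome share one boundary. Applying the inclusive limits to the outcome alone would count a patient enrolled at 93% and still at 93% as having progressed. The lack of a sentence explaining the strict signs is only an editorial matter.

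**Conclusion.** The point holds in a limited form. The primary endpoint omits escalation of respiratory support, does not tie saturation to support, and relies on a P/F value that may not exist. Some escalated patients can be counted as successes. Each is worth 1 point at n = 100, 2 at n = 50 and 4 at n = 25. The number affected is not in the documents and is probably small, because four conditions must hold together. The assumed values of 1, 5 and 10 patients show a range, not an estimate.

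The documents do not support the inference that ventilated patients would routinely be scored as successes, or that the reported rate will be materially inflated. This is a cheap improvement of minor severity, not an error in the endpoint.

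**What to change.** Leave eligibility and the primary endpoint as they are. Add to section 11.1:

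1. One prespecified sensitivity analysis of the response rate, using the Oxygen Use and Ventilator fields, in which a new start of high-flow oxygen, non-invasive ventilation or mechanical ventilation after infusion also counts as progression. A small increase in flow does not count.
2. Judge a new start against support on the infusion day, because patients already on oxygen may enrol. State one rule for entries dated on the infusion day, for example that they count as baseline, and use it for both the primary and the sensitivity rate.
3. Report beside the two rates how many patients had any P/F value, so that readers can see how far the result depends on blood gases being drawn.

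The cost is a little extra tabulation from fields already on the form. The downside for the sponsor is that the sensitivity rate can only be equal to or lower than the primary rate.
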